8.1.3 Selection of test method and reasons

This clinical trial is a "prospective, multi-center, stratified-block randomization, incomplete blinding, parallel

positive control, non-inferiority test".

- (1) Prospective: A research method that tracks from the present to the future. Prospective studies can clarify the causal relationship; uniform diagnostic, detection, and evaluation criteria can be available for the obtained data, the data processing therefore is controllable.
- (2) Multi-center: 5 clinical trial institutions were selected to conduct this clinical trial. The application of multi-center trial can allow to obtain more cases than those of single-center trial in the same time, the clinical trial time therefore can be shortened; since the multi-center trial is completed by different regions, different trial centers and many clinical researchers, the conclusion therefore is often widely representative.
- (3) Stratified block randomization: This trial adopts the stratified block randomization method (with the study site as the stratification factor) and the randomization envelope to randomize the subjects who are screened successfully. The randomized-grouping time is when the subjects sign the ICF, which also meets the inclusion and exclusion criteria in the protocol at the same time. Randomized grouping ensures that, except for treatment factors, other non-treatment factors that may have confounding effect are kept consistent in each group as far as possible, so as to ensure the balance of baseline of each group; randomized-grouping allows each subject to have equal opportunity to be assigned to the test group or control group.
- (4) Incomplete blinding: Since the investigational medical device and the control medical device are different in appearance, while the subjects are under anesthesia during the operation, the grouping arrangement can not be known. Therefore, the method of incomplete blinding is used, that is, the investigators knows the grouping result, while the subject does not know the grouping result. The blinding method can minimize the bias caused by "placebo effect" and investigator bias; for the less precise observation indicators, it can significantly reduce the bias; and make the evaluation of adverse reactions by investigators and subjects more objective.

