8.1.15 Effectiveness evaluation method

8.1.15.1 Main effectiveness evaluation indicators, method and time for evaluation, recording and analysis

(1) Success rate of anastomosis

Justification for selection: According to the *Guidelines for Technical Review of Endoscopic Stapler Registration* issued by NMPA (original CFDA) on March 13, 2017, the "success rate of anastomosis" is selected as the primary evaluation indicator for such products.

Evaluation time: During the surgery.

Evaluation site: Tissues receiving linear stapler for gastrointestinal anastomosis.

Evaluation method: The transection and anastomosis of lung tissues are performed during the operation. The device is withdrawn after successful triggering. The cutting staple line is carefully checked for integrity, air leakage and bleeding. Anastomosis is considered as successful if all anastomotic rings are intact without leakage or bleeding, otherwise it is considered as failure. If necessary, the gas injection method is used to inspect whether there is bubble overflow at anastomotic stoma. If there is no bubble overflow, it is recorded as successful anastomosis; if there is obvious bubble overflow, it is recorded as anastomosis failure.

Formula: Anastomosis success rate = number of subjects with successful anastomosis in each group/total number of subjects in this group \times 100%

Precautions: During gastrointestinal tissue cutting and anastomosis, the subject may be converted into thoracotomy due to his complicated condition. At this time, the investigators need to determine whether the subject's conversion to thoracotomy is caused by the stapler. If it is caused by the stapler, it is judged as anastomosis failure. After gastrointestinal tissue anastomosis, the investigator may need to supplement the stitching treatment for anastomotic tissues. If the supplement is resulted from incomplete anastomosis ring, leakage and bleeding, it is considered as anastomosis failure.

8.1.15.2 Secondary effectiveness evaluation indicators, method and time for evaluation, recording and analysis

(1) Stapler-resulted conversion rate

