Justification for selection: The need for conversion to thoracotomy due to failed anastomosis increases the risk to the subject. Therefore, the "stapler-resulted conversion rate" is selected as one of the effectiveness indicators of the product. At the same time, with reference to the *Guidelines for Technical Review of Endoscopic Stapler Registration* issued by NMPA (original CFDA) on March 13, 2017, the "stapler-resulted conversion rate" is selected as an effectiveness evaluation indicator for such products.

Evaluation time: During the surgery.

Evaluation method: Indicators of conversion to laparotomy are ① bleeding difficult to control; ② invasion of adjacent organs or blood vessels resulting in difficulty in surgery; ③ patients difficulty in tolerating pneumoperitoneum during surgery; ④ accidental injury of other organs during surgery, which are difficult for treatment; ⑤ severe intraoperative adhesions found during surgery. If the conversion to laparotomy is caused by the stapler, it should be recorded truthfully.

Formula: Stapler-resulted conversion rate = number of eligible subjects in each group/total number of subjects in this group \times 100%

(2) Number of stitches repaired with staple line

Justification for selection: When the stapler is used for gastrointestinal tissue anastomosis, the situation that

the staple line needs to be repaired may occur. When the number of repair needles becomes larger, it may increase the risk to the subject. Therefore, the "number of stitches repaired with staple line" is selected as one of the indicators to evaluate the effectiveness of the product. At the same time, with reference to the *Guidelines for Technical Review of Endoscopic Stapler Registration* issued by NMPA (original CFDA) on March 13, 2017, the "number of stitches repaired with staple line" is selected as an effectiveness evaluation indicator for such products.

Evaluation time: During the surgery.

Evaluation method: The number of staple line repair needles of each subject during operation is recorded.

Precautions: Anastomotic repair is required when the anastomotic ring is incomplete, leaking and bleeding. Anastomotic repair may also be necessary when there is a dehiscence of the staple line during surgery. Sometimes the investigators may perform anastomotic repair in order to strengthen the anastomotic site. Therefore, the reasons for repair should be recorded.

(3) Operation time

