8.2.4 Blinding method

The investigators could not be blinded due to the difference in appearance between the test device and the control device, this trial therefore adopted an incomplete blinding method, and the subjects were not informed of the randomization results (i.e., the subjects did not know their own treatment assignment).

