- (2) Observation of the study product⁹: whether the digestive tract is successfully transected and stapled, whether the cutting anastomosis ring/staple line is complete, whether there is leakage of cutting anastomosis ring/staple line, whether there is bleeding of cutting anastomosis ring/staple line, whether there is bubble overflow at the anastomotic stoma¹⁰, whether there are indicators of conversion to laparotomy¹¹, number of needles for anastomotic repair¹¹, whether there is anastomotic dehiscence¹¹, whether there are other complications¹¹, whether the staple line or tissue buttressing materials are used, and the operating performance of stapler;
- (3) Device use¹²: model and specification of electric stapler, model of cartridge, use condition¹³, cutting and stapling tissues¹⁴, device defects;
- (4) Postoperative follow-up observation: first anus exhaust time, semi-liquid feeding time, first defecation time, bowel sound recovery time, whether there is anastomotic bleeding¹⁵, whether there is anastomotic leakage¹⁵, whether there is anastomotic stenosis¹⁵, whether there are other complications¹⁵, whether there is abdominal effusion and the abdominal effusion volume;
- (5) Routine observation items: adverse events, concomitant medication, protocol deviations.

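### For an oversewn staple line, the unblinded operator's findings and stated reason decide whether the stitching counts as failure; no analysis tests this, and the stitch-count endpoint pools elective with defect stitches

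*Combined protocol and SAP*

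**What the plan says.** **Who scores.** Section 8.2.4 states: "The investigators could not be blinded due to the difference in appearance between the test device and the control device". Section 8.1.3 (4) confirms that "the investigators knows the grouping result, while the subject does not know the grouping result". The primary endpoint is evaluated during surgery (8.1.15.1), and no masked or independent assessor is named.

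**How success is scored.** The main rule in 8.1.15.1 rests on inspection after the device is withdrawn: "Anastomosis is considered as successful if all anastomotic rings are intact without leakage or bleeding, otherwise it is considered as failure". The gas test is optional: "If necessary, the gas injection method is used to inspect whether there is bubble overflow at anastomotic stoma". Obvious bubble overflow and a conversion caused by the stapler are also failures. A precaution then covers added stitches: "If the supplement is resulted from incomplete anastomosis ring, leakage and bleeding, it is considered as anastomosis failure".

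**Stitches as a secondary endpoint.** Section 8.1.15.2 (2) defines the measure: "The number of staple line repair needles of each subject during operation is recorded". Its precautions give three grounds for repair: a ring that is incomplete, leaking or bleeding; dehiscence of the staple line during surgery; and reinforcement ("Sometimes the investigators may perform anastomotic repair in order to strengthen the anastomotic site"). They ask for the reason to be recorded. Footnote 11 to 8.2.5.5 (2) also asks for the reason and whether it relates to the stapler. Section 9.7.1 compares measurement data by t-test or Wilcoxon test and mentions no split by reason.

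**Buttressing.** It lies within the applicable scope of both devices (6.1, 7.1). Section 8.2.5.5 (2) records "whether the staple line or tissue buttressing materials are used". No rule links it to success or failure, and no comparison by arm is specified.

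**The concern.** Three gaps follow.

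1. The main non-inferiority conclusion rests on intraoperative judgements by someone who knows the arm. Where stitches have been added, that person also supplies the reason that settles their status. Masking the subject, which 8.1.3 (4) credits with reducing investigator bias, does not reach an endpoint that the operator scores.
2. The stitch count is justified in 8.1.15.2 (2) as a marker of risk from lines that need repair. Stitches added to sound lines raise the count without saying anything about line quality. If reinforcement habits differ between arms, the comparison partly measures habit.
3. The two sections do not match. Section 8.1.15.2 (2) lists dehiscence as a ground for repair, while the stitching precaution in 8.1.15.1 does not name it. The status of a line stitched for dehiscence then depends on whether it is also recorded as an incomplete ring, a leak or a bleed.

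**Working it through.** **1. The plan's sample size (9.2.1).** Inputs: success 97% in both arms, margin 10%, one-sided alpha 0.025, power 80%, dropout 20%.

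- Base formula: (2 × 0.97 × 0.03) × (0.8416 + 1.9600)² / 0.10² = 45.68, rounded up to 46.
- Correction formula: (46/4) × (1 + √(1 + 4/(0.10 × 46)))² = 64.4, rounded up to 65.
- Dropout: 65/0.80 = 81.25, rounded up to 82 per arm, or 164 in total.

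The plan's 65, 82 and 164 all reproduce, and this point does not affect them.

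**2. How few cases decide the result.** Section 9.5 requires the lower 95% limit of the difference to exceed -10%. The plan does not name the interval method; Miettinen-Nurminen is used here. The most test-arm failures that still pass are:

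| Control failures | 82 per arm | 65 per arm |
|---|---|---|
| 0 | 2 | 1 |
| 1 | 3 | 2 |
| 2 | 4 | 2 |
| 3 | 4 | 3 |

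**3. Illustration of differential classification.** Assume true success of 87% (test) and 97% (control), exactly at the margin. Let a share f of test-arm failures be recorded as elective strengthening and scored as success, with the control arm recorded correctly. Apparent test success is 1 − 0.13 × (1 − f), which is 0.870, 0.883 and 0.9025 for f = 0, 10% and 25%. Exact binomial enumeration gives these chances of a false non-inferiority finding:

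| Interval | n per arm | f = 0 | f = 10% | f = 25% |
|---|---|---|---|---|
| Miettinen-Nurminen | 82 | 2.1% | 4.2% | 10.6% |
| Miettinen-Nurminen | 65 | 1.8% | 3.3% | 7.7% |
| Newcombe | 82 | 2.1% | 4.2% | 10.7% |
| Newcombe | 65 | 2.3% | 4.1% | 9.6% |
| Wald | 82 | 4.3% | 8.0% | 18.6% |
| Wald | 65 | 4.1% | 7.2% | 15.7% |

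If the same share is relabelled in both arms (82 per arm, Miettinen-Nurminen), the figures are 3.6% at f = 10% and 7.6% at f = 25%, because equal relabelling shrinks the observed difference.

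The documents give no rate of reinforcement or misclassification, so every f above zero is an assumption. The model applies f to all test-arm failures, although only stitched cases could be relabelled this way.

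**4. The stitch count.** This needs no arithmetic. The definition in 8.1.15.2 (2) takes every repair stitch, the same section collects the reason, and 9.7.1 does not use it for this endpoint.

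**The case against.** A reader might infer that the surgeon's stated reason alone decides success or failure. The documents do not support that. Under the main rule in 8.1.15.1, a line that is incomplete, leaking or bleeding is a failure whatever reason is given for the stitches. Section 8.2.5.5 (2) records ring completeness, leakage, bleeding and bubble overflow separately from repair stitches, so a false success would need those entries to agree with the label.

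Four further objections stand in whole or part:

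- **Order of events.** Section 8.1.15.1 already places inspection after the device is withdrawn and treats added stitching separately. What is missing is an explicit statement that scoring uses the findings before stitching.
- **Use of reasons.** The primary endpoint does use the repair reason; only the stitch count ignores it. Section 9.1 refers to a separate statistical analysis plan, to be finalised before database lock. Its text is not in the material reviewed, and it could add a split.
- **Buttressing.** No reason rule applies to it, so it cannot be part of a relabelling argument. The gap is only that its use by arm is not reported.
- **Direction and size.** Reinforcing a line already found intact and dry leaves the primary outcome unchanged. An unblinded operator could equally over-report defects in the test arm. Conversion failures cannot be relabelled this way. That one case can reverse a result at its boundary is true of any small binary comparison and is not evidence of bias.

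The separate inspection items do not close the gap, because the same unblinded operator makes those findings and the gas test is optional.

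**Conclusion.** The concern holds in limited form. An unblinded operator scores the primary endpoint. For oversewn lines, that operator's findings and stated reason settle whether the stitching counts as failure, and no stated analysis shows how sensitive the conclusion is to this. The stitch-count endpoint mixes elective and defect stitches although the data to separate them are collected. The two sections disagree on dehiscence.

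The false non-inferiority figures show scale only. They rest on true success of 87% against 97%, on the interval method chosen, and on assumed relabelling shares that no document supports. The documents do not show that misclassification will occur or which arm it would favour. This is a worthwhile, inexpensive improvement to endpoint definition and a bias check; it does not show that the design is invalid.

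**What to change.** 1. **Stitch count (8.1.15.2 (2), 9.7.1).** Define the endpoint as stitches placed for a recorded defect. Report elective reinforcement stitches and buttress use separately, by arm.
2. **Supportive analysis (9.7.1 or the separate analysis plan).** Pre-specify one analysis of the primary endpoint in which any supplementary stitch on a trial staple line counts as failure in both arms. Label it a sensitivity check, because the 97% rate and the 10% margin were not set for that definition.
3. **Scoring rule (8.1.15.1).** State that the primary endpoint is scored on the integrity, leakage and bleeding findings at the post-firing inspection, before stitching, whatever reason is later given. This is a rule about which findings are scored. It must not delay treatment, and whether to reinforce remains the surgeon's decision.
4. **Dehiscence.** Reconcile 8.1.15.1 with 8.1.15.2 (2) on how a line stitched for dehiscence is classified.

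**Cost.** Wording changes and one extra table, with no change to sample size. The supportive success rate will be lower and will partly reflect elective reinforcement. The same unblinded operator still makes the findings, so these steps expose the bias and do not remove it.

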Justification for selection: The main purpose of stapler is to reduce the surgeon's operation intensity and save operation time. Therefore, the operation time is selected as one of the indicators to evaluate the product performance. Meanwhile, with reference to the *Guidelines for Technical Review of Endoscopic Stapler Registration* issued by NMPA (original CFDA) on March 13, 2017, the "operation time" is selected as the secondary evaluation indicator for such products.

Evaluation time: During the surgery.

Evaluation method: The investigators record the time taken from thoracotomy to chest closure to the nearest minute.

(4) Anastomosis time

Justification for selection: The main purpose of stapler is to reduce the surgeon's operation intensity and save operation time. Therefore, the stapling time is selected as one of the indicators to evaluate the product performance. Meanwhile, with reference to the *Guidelines for Technical Review of Endoscopic Stapler Registration* issued by NMPA (original CFDA) on March 13, 2017, the "anastomosis time" is selected as the secondary evaluation indicator for such products.

Evaluation time: During the surgery.

Evaluation method: The investigators record the time taken for the subject to perform the transection from the completion of mobilization of gastrointestinal tissues (the first operation site) to the completion of anastomosis of gastrointestinal tissues. The time is accurate to minutes.

(5) Anastomotic healing time

Justification for selection: Anastomotic healing is an important indicator for effectiveness and safety

evaluation of such products. Therefore, the anastomosis time is selected as one of the indicators to evaluate the product performance. Meanwhile, with reference to the *Guidelines for Technical Review of Endoscopic Stapler Registration* issued by NMPA (original CFDA) on March 13, 2017, eventually, the "anastomotic healing time" is used as a secondary indicator for evaluation.

Evaluation time: After surgery.

Evaluation method: The recovery of borborygmus and smooth eating and defectaion are considered as anastomotic healing. Only when the subjects meet these three criteria, it can be judged as the anastomotic healing, and the latest time observed shall be the basis for evaluation. The time is accurate to day.

(6) Time of first flatus

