Technical Review of Endoscopic Stapler Registration issued by China Food and Drug Administration on March 13, 2017, the "incidence of anastomotic leakage" is selected as a safety evaluation indicator for such products.

Evaluation time: From the end of surgery to the end of follow-up.

Evaluation method: Patients with at least one of the following items are considered as anastomotic leakage: A. imaging examination, such as gastrointestinal radiography, confirms anastomotic leakage; B. fecal substances appearing in the abdominal drainage tube or incision, in which other sources of intestinal tract can be excluded; C. reoperation exploration confirms anastomotic leakage; D. abdominopelvic abscess beside the anastomosis. Anastomotic leakage is divided into 3 grades according to the severity: Grade A: no special treatment is required; Grade B: active treatment is required, but no reoperation is required; Grade C: reoperation is required.

Formula: Incidence of anastomotic leakage = eligible subjects in each group/total number of subjects in this group \times 100%

Precautions: Necessary records should be kept for the treatment of anastomotic leakage.

(4) Incidence of anastomotic stricture

Justification for Selection: Anastomotic stricture is a common complication of gastrointestinal anastomosis, which will increase risks to subjects. Therefore, "the incidence of anastomotic stricture" is selected as one of the indicators to evaluate the product safety.

Evaluation time: From the end of surgery to the end of follow-up.

Evaluation method: The clinician judges whether the subject has an anastomotic stricture based on the symptoms, signs, endoscopy, angiography, etc.

Formula: Incidence rate of anastomotic stricture = eligible subjects in each group/total number of subjects in the group \times 100%

(5) Incidence of anastomotic stricture infection

Justification for Selection: Anastomotic stricture infection is a common complication of gastrointestinal anastomosis, which will increase risks to subjects. Therefore, "the incidence of anastomotic stricture infection" is selected as one of the indicators to evaluate the product safety.

Evaluation time: from the end of surgery to the end of follow-up.

Evaluation method: The clinician judges whether the subject has a staple line infection based on the symptoms, signs, endoscopy, angiography, etc.

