14.1.5 Handing protocol of adverse events that may occur in this clinical trial

- (1) Anastomotic bleeding: It is related to the factors of anastomotic leakage. The bleeding is generally the technical factor. The prevention is mainly to avoid the tension at the anastomotic stoma and the fat drop left at the cutting site.
- (2) Anastomotic leakage: The incidence of anastomotic leakage is reported to be 4% to 15% in the literature. It may be caused by the stapler, or related to the patient's condition or the doctor's operation;
- (3) Anastomotic stricture: It is one of the most common complications, mostly occurring after 1 month after surgery.
- (4) Major incisional bleeding: Drop in hemoglobin $\geq 20g/l$ resulting in ≥ 1 transfusion.
- (5) Minor incision bleeding: Bleeding that does not meet the criteria for "severe bleeding".
- (6) Incision site infection: Infection at the incision site due to improper nursing, resulting in prolonged incision healing time, prolonged suture removal time, or unplanned antibiotic therapy.
- (7) Delayed healing of incision: The incision in contact with suture has delayed healing time.
- (8) Anemia and hypoproteinemia: Symptoms caused by tumor deterioration in patients with gastric cancer;
- (9) Tumor recurrence or metastasis: Symptoms caused by further tumor deterioration in patients with gastric cancer;

(10) Gastrointestinal discomfort symptoms: Common symptoms of gastrointestinal diseases, such as nausea, belching, constipation, diarrhea, acid reflux, abdominal pain, etc.

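### Anastomotic healing time is dated from bowel function alone, so a subject with a postoperative leak can be recorded as healed or drop out of the endpoint, but is never counted as unhealed

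*Combined protocol and SAP*

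**What the plan says.** Section 8.1.15.2(5) makes anastomotic healing time a secondary effectiveness indicator, justified by the importance of healing for both effectiveness and safety. The rule is: "The recovery of borborygmus and smooth eating and defectaion are considered as anastomotic healing". All three markers are required ("Only when the subjects meet these three criteria, it can be judged as the anastomotic healing"), and on timing "the latest time observed shall be the basis for evaluation. The time is accurate to day". The rule mentions no leakage, imaging, endoscopy or reoperation.

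Leakage is a separate safety indicator in 8.1.16(3), assessed from the end of surgery to the end of follow-up. "Patients with at least one of the following items are considered as anastomotic leakage": imaging confirmation, faecal drainage, confirmation at reoperation, or an abscess beside the anastomosis. It is graded: "Grade A: no special treatment is required; Grade B: active treatment is required, but no reoperation is required; Grade C: reoperation is required".

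Other sections that bear on a leak case:

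- 8.2.5.5(4) lists the postoperative items recorded, among them "first anus exhaust time, semi-liquid feeding time, first defecation time, bowel sound recovery time", together with leak status.
- 8.2.7.4 lists healing time and leakage side by side at Visit 4, with no rule linking them.
- 8.1.16(6) classes anastomosis-related adverse events as serious.
- 8.1.12(2)(c) says that a subject with a serious adverse event should be withdrawn.
- 9.7.2(4) does not impute missing secondary values.
- 9.5 reads p > 0.05 on a secondary indicator as no significant difference in that indicator.

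**The concern.** The indicator is named and justified as a measure of the anastomosis, but it is scored from return of bowel function. The two can part in exactly the subjects where healing is in doubt. The leakage record neither resets nor voids the healing date, and no provision is made for a subject who does not heal.

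What is at stake is how the result may be read. The trial supports a registration application. A finding of no significant difference in healing time could be taken as evidence that anastomoses heal equally well with both devices. The endpoint as defined cannot support that, because leak cases enter it either as healed or not at all.

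**Working it through.** **The plan's own figure.** No figure is given for healing time. The sample size in 9.2.1 rests on the intraoperative success rate and reproduces:

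- Base: n = 2 × 0.97 × 0.03 × (1.960 + 0.842)² / 0.10² = 45.7.
- Correction: (n/4) × [1 + √(1 + 4/(0.10 × n))]² = 64.1 with n = 45.7, or 64.4 with n = 46, so 65 per group.
- Dropout: 65 / 0.80 = 81.25, so 82 per group and 164 in total.

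Healing time does not enter this calculation.

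**Routes for a subject with a leak, from the sections side by side.**

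1. *Leak confirmed after the three markers return.* For illustration: bowel sounds on Day 2, eating on Day 4, defecation on Day 5, leak confirmed on Day 7. Under 8.1.15.2(5) the healing date is Day 5. Under 8.1.16(3) the subject is a leak case. Nothing in 8.2.7.4 or 9.7 revises the Day 5 date.
2. *Grade A leak in a subject who meets all three markers.* Grade A needs no special treatment, so functional recovery is possible while the leak is present. Section 8.1.12 asks for evaluations that can be completed to be completed, and 14.1.3 continues follow-up to the event's outcome or the end of the trial. A healing date can therefore still be recorded.
3. *Leak found before the markers return.* The event is serious under 8.1.16(6), and 8.1.12(2)(c) calls for withdrawal. Healing time may then be missing, and 9.7.2(4) leaves it missing.

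Routes 1 and 2 give a healed value. Route 3 gives no value. None gives an unhealed value, and the t test or rank-sum test in 9.7.1 has no stated place for one.

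**How many subjects could be exposed.** Section 14.1.5(2): "The incidence of anastomotic leakage is reported to be 4% to 15% in the literature".

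| Subjects per arm | at 4% | at 15% |
|---|---|---|
| 82 (enrolled) | 82 × 0.04 = 3.3 | 82 × 0.15 = 12.3 |
| 65 (before dropout allowance) | 65 × 0.04 = 2.6 | 65 × 0.15 = 9.8 |

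The chance of at least one leak among 82 at the 4% rate is 1 − 0.96⁸² = 96.5%, so the gap is likely to be met in practice.

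These are expected leak cases, hence a ceiling on contradictory healing dates. The documents do not split leaks by grade or by timing relative to bowel function, so the share following each route cannot be derived.

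**What the endpoint would miss.** As a hypothetical only, put the two ends of the cited range in the two arms: 12.3 − 3.3 = 9 more leak cases in one arm. None of the 9 would be scored as a failure to heal.

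**The case against.** The strongest reply is that the documents do handle leaks. The three markers are demanding: eating must be smooth, and a leak may delay or prevent that. A leak recognised early is a serious adverse event and leads towards withdrawal, so it gives a missing value and not a false one. Leakage has its own graded indicator and its own between-arm test, and leaks also count among serious adverse events, so an excess would be seen there. Section 9.5 confines its statement to the indicator tested. Healing time is recorded as its own Visit 4 item, when an early leak would already be known.

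Much of this stands, and it rules out several stronger readings:

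- A reader might infer that every subject with a leak is recorded as healed. The text supports only that such a subject can be.
- A reader might take 3 to 12 per arm as the number with a false date. It is an upper bound.
- A reader might infer that the indicator only repeats first bowel movement and semi-liquid diet, plus bowel sounds. No item for smooth eating appears in 8.2.5.5(4), but the case report form is not in the documents, so how that criterion is recorded is unknown.
- A reader might infer that the trial would overlook an excess of leaks. The separate leakage indicator answers that.
- A reader might want dehiscence treated in the same way. Section 8.1.16(1) assesses it during surgery, so it does not belong in a postoperative healing rule.

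What the reply does not answer is that missing values from early leaks do not repair the endpoint. They remove unfavourable cases from it.

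**Conclusion.** The concern holds in limited form. As written, healing time measures return of bowel function, and a subject with a postoperative leak is either given a healing date or may leave the endpoint. A device with more leaks could show no significant difference on this indicator, and that result should not be read as equal healing.

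The ceiling is about 3 to 12 of 82 subjects per arm. It assumes that the cited 4% to 15% applies to this population and that every leak case is affected, which the documents do not show. The damage is confined to one secondary indicator and to conclusions about healing. The primary endpoint, the sample size and the leakage indicator are untouched.

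**What to change.** Preferred: state the following in 8.1.15.2(5) and the statistical analysis plan.

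- A subject with postoperative anastomotic leakage, or reoperation at the anastomosis, is not healed on the bowel-function date.
- That subject's date is the later of functional recovery and the recorded resolution date of the event.
- A subject whose event is unresolved at last follow-up, or who was withdrawn because of it, counts as not healed.
- The arms are compared by the Wilcoxon rank-sum test already allowed in 9.7.1, with unhealed subjects ranked worst. The synopsis names only the t test for secondary measurement data and needs matching wording.

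Alternative: rename the indicator 'time to recovery of gastrointestinal function' and draw no healing conclusion from it.

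Either way, 8.1.12, 8.1.15.2(5), 8.1.16(3), 8.1.16(6) and 9.7.2 must be reconciled on how leak cases enter this endpoint. This concerns scoring only and takes no position on when a subject should be withdrawn.

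The cost is wording and minor programming. Leak status and recovery dates are recorded under 8.2.5.5(4) and event end dates under 14.1.3, and 9.1 leaves the analysis plan open until database lock. One small downside: the resolution date rests on the adverse event record, because postoperative contrast and endoscopic imaging is at the investigator's discretion (note 8 to 8.2.5.4).
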